4. RESEARCH QUESTIONS AND OBJECTIVES

The primary study objective is to evaluate the impact of the risk minimization measures on HCP and patient understanding regarding the risk of hypoglycemia and/or hyperglycemia due to medication errors associated with administration of Humalog U-200 KwikPen as communicated through the risk minimization measures.

The secondary objective is to evaluate behavior of HCPs and patients regarding the risk of hypoglycemia and/or hyperglycemia due to medication errors associated with administration of Humalog U-200 KwikPen as communicated through the risk minimization measures.

Specifically, this protocol refers to the surveys that are designed to assess the effectiveness of communications to HCPs and patients by assessing their understanding of the risks and safe use of Humalog U-200 KwikPen which were communicated through risk minimization measures including the following key safety messages:

HCPs:

- It is not necessary to adjust the insulin dose when switching from one strength of Humalog to the other
- Humalog U-200 KwikPen should not be transferred from the KwikPen to a syringe or insulin pump
- It is necessary to specify the Humalog strength on prescriptions
- It is necessary that patients always have a backup pen

Patients:

- It is not necessary to adjust the insulin dose when switching from one strength of Humalog to the other
- Humalog 200 units/mL should not be transferred from the KwikPen to a syringe as this could result in SEVERE OVERDOSE
- It is always necessary to carry a backup pen

The surveys are also designed to answer the following process research questions to assess the effectiveness of communications to HCPs and patients through the risk minimization measures. By testing a representative population about their knowledge and understanding of key safety message themes, we can generalize the:

HCPs:

- Extent of understanding of the key safety messages for Humalog U-200 KwikPen, as communicated through the DHPC (Were the key safety messages communicated in the DHPC understood by the HCP?)

- Extent of discussion between HCPs and patients when initially prescribing or dispensing Humalog U-200 KwikPen (Did the HCP convey the key safety messages in the label and DHPC to patients when they received their initial prescription of Humalog U-200 KwikPen?) with reference to the key safety messages.

Patients:

- Extent of understanding of the key safety messages for Humalog U-200 KwikPen, as communicated through risk minimization measures (Were the key safety messages in the patient communication understood by the patient?)
- Extent of recall/receipt of the patient communication in the patient sample upon first prescription of Humalog U-200 KwikPen (Does the patient recall receiving the patient sample which included the patient communication document?)
- Extent of key safety message consideration by patients during administration of Humalog U-200 KwikPen (Will the patient follow the key safety messages communicated during administration of Humalog U-200 KwikPen?)

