5.7. Study size

The target sample sizes for the HCP and patient populations are 280 completed surveys for each population. The size of the sample was determined based on both practical and statistical considerations. There is no target comprehension rate specified *a priori*. A sample of 280 completed surveys for both HCPs and patients will allow estimation of the comprehension rate for each key safety message with a moderately high degree of precision. The table below shows the precision of the estimates for level of understanding using two-sided 95% CIs obtained with the sample size of 280 completed surveys. The noted CIs are used to indicate that for any survey-estimated rate of understanding, the true population rate of understanding is at least as high as the lower limit of the 95% CI and may be as high as the upper limit of the 95% CI.

Equation 1

$$95\%CI = Response\ Rate \pm 1.96 \left\{ \sqrt{\left[\frac{Response\ Rate(1-Response\ Rate)}{Sample\ Size} \right]} \right\}$$

Table 1 Sample size calculations

Sample Size	Observed Response Rate* (e.g. Knowledge)	2-Sided 95% CI		
		Half-width	Lower Limit	Upper Limit
280	50%	5.9%	44.1%	55.9%
	60%	5.7%	54.3%	65.7%
	70%	5.4%	64.6%	75.4%
	80%	4.7%	75.3%	84.7%
	90%	3.5%	86.5%	93.5%

*Percentage of responders who correctly answered a question.

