5.9. Data analysis

Data collected from the survey will be reported as descriptive statistics. Frequency distributions with 95% CIs will be calculated for respondent responses to all questions that address the survey objectives. Responses to each question relating to the key safety messages will be categorized as “Correct response” and “Incorrect response”. “I don’t know” is categorized as an incorrect response unless otherwise specified.

In addition to the overall analysis, survey data will be analyzed to determine if there are any differences for HCPs, by medical specialty.

The following will be reported as part of the analysis:

HCPs:

Survey administration

- The number of survey invitations issued by method of distribution and specialty

- The number of survey invitations returned due to incorrect mailing address of HCPs invited to participate in the survey
- The number of HCPs who responded to the invitation to participate in the survey
- The number of HCPs eligible for participation in the survey
- The number of ineligible HCPs along with the reasons for ineligibility
- The number of eligible HCPs who completed the survey

Demographic characteristics of participants

- Distribution of participants by age groups
- Distribution of participants by gender
- Distribution of participants by practice setting
- Distribution of HCP by state
- Distribution of participants by medical specialty
- Distribution of participants by years in medical practice
- Distribution of participants by number of patients treated with Humalog U-200 KwikPen

Responses to questions pertaining to the survey objectives:

- Awareness of the DHPC on the correct use of Humalog U-200 KwikPen
- Understanding of the key safety messages
- Self-reported practices with respect to communication of the key safety messages in clinical practice

Patients:

Survey administration

- The number of invitations distributed
- The number of survey invitations returned due to incorrect mailing address of patients invited to participate in the survey
- The number of patients who responded to the invitation to participate in the survey
- The number of patients eligible for participation in the survey
- The number of ineligible patients along with the reasons for ineligibility
- The number of eligible patients who completed the survey

Demographic characteristics of participants

- Distribution of participants by age groups
- Distribution of participants by gender
- Distribution of patient by state

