5.11. Limitations of the research methods

The participants will be self-selected since they will voluntarily respond to the invitation to participate. The survey recruitment strategies will include a random sample of HCPs who received educational outreach, which should be generalizable to the overall HCP population who are educated about the use of Humalog U-200 KwikPen.

Patients will be recruited via the PBM database and will be identified as those patients who have filled/refilled a prescription for Humalog U-200 KwikPen.

Additionally, inherent in survey research is the reliance on the respondent's recall for whether or not the risk minimization communication was received in order to evaluate the scope of risk minimization measures. If the respondent says she/he did not receive the communication, the risk minimization program is evaluated as not optimally disseminating material. It is possible, however, that respondents may simply not recall receiving the tools that were, in fact, received. It is also possible that they have acceptable understanding of the risks and appropriate behaviors despite not receiving or recalling receipt of the risk minimization measure-specific communication. All data from the survey are self-reported and therefore susceptible to possible reporting bias. This is also applicable to the patients' self-reporting of their practice behaviors to minimize the risks. There may be discrepancies between what respondents report about their practices and their actual behaviors.

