[DROP DOWN LIST INPUT WITH STATES TABLE, EXCLUDE PREFER NOT TO ANSWER]

[IF RESPONDENT ANSWERS MASSACHUSETTS, MINNESOTA, VERMONT, OR DISTRICT OF COLUMBIA, DISPLAY REMINDER MESSAGE 1 ON SAME PAGE AND GO TO Q4.]

[REMINDER MESSAGE 1]: If you practice and you are licensed in the District of Columbia, Massachusetts, Minnesota, or Vermont just a reminder that we appreciate your participation; however, no compensation for your services will be provided in accordance with local laws.

4. Please choose an option about your participation in this survey.
 - i. ○ I will participate in the survey and provide my contact information.
 - ii. ○ I will participate in the survey but choose not to be paid.

5. Are you involved in the management of patients with diabetes? This includes prescribing medications to treat diabetes or providing education to help manage diabetes.
- Yes
 - No **[GO TO Q7, TERMINATE AFTER Q14]**
6. What is your role in the management of patients with diabetes?
- Physician
 - Nurse Practitioner
 - Physician Assistant
 - Registered Nurse **[GO TO Q8]**
 - Other **[GO TO Q8]**
7. What is your primary medical specialty?
- General Internal Medicine
 - Endocrinology/Diabetology
 - Family Medicine
 - Other
8. How many years have you been in practice as a physician, physician assistant, or nurse since completing your medical/nursing education?
- Less than 5 years
 - 5 – 10 years
 - 11 – 15 years
 - More than 15 years

9. In what type of facility do you work?
- General Practice
 - Hospital
 - Other
10. Are you aware of the insulin product Humalog® U-200 KwikPen®?
- Yes
 - No **[GO TO Q12, TERMINATE AFTER Q14]**
 - I don't know **[GO TO Q12, TERMINATE AFTER Q14]**
11. For how many patients have you prescribed, or managed their treatment with, Humalog® U-200 KwikPen®?
- 0 **[TERMINATE AFTER QUESTION 14 IF 140 OR MORE COMPLETE RESPONDENTS HAVE ANSWERED 0, WHERE 140 IS A CONFIGURABLE NUMBER]**
 - 1 – 5
 - 6 – 10
 - 11 – 20
 - More than 20

12. Have you or any of your immediate family members ever worked for Eli Lilly and Company (Lilly), United BioSource Corporation (UBC), or the Food and Drug Administration (FDA)?

- Yes **[TERMINATE AFTER QUESTION 14]**
- No
- I don't know **[TERMINATE AFTER QUESTION 14]**

13. Which of the following groups best describes your age?

- Less than 30
- 30 – 39
- 40 – 49
- 50 – 59
- 60 – 69
- 70 or older

14. What is your gender?

- Male
- Female

[END SCREENING QUESTIONS]

[BEGIN SURVEY CONTENT]

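### The protocol claims a representative sample and a bound on the population rate, but completers are self-selected and a quota stated only in the HCP questionnaire can move the pooled HCP rate

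*Protocol*

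**What the plan says.** **The claim.** Section 4 introduces the research questions for both surveys with "By testing a representative population about their knowledge and understanding of key safety message themes, we can generalize the" extent of understanding, discussion and recall. Section 5.1 says that the participating samples will show whether the target populations know and follow the messages. Section 5.7 sets the size ("The target sample sizes for the HCP and patient populations are 280 completed surveys for each population"), gives in Table 1 the "precision of the estimates for level of understanding using two-sided 95% CIs obtained with the sample size of 280 completed surveys", and then explains the interval: "the true population rate of understanding is at least as high as the lower limit of the 95% CI".

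**The sample.** Section 5.11 states: "The participants will be self-selected since they will voluntarily respond to the invitation to participate". Its next sentence nevertheless describes the random sample of HCPs as one "which should be generalizable to the overall HCP population who are educated about the use of Humalog U-200 KwikPen". Under Section 5.4 the random draw is of HCPs to be recruited from the list of those sent the DHPC. Patients are invited from one pharmacy benefits manager's fill records, and no random draw is described for them. Section 6.2 restricts the analysis to completed surveys.

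**The quota.** In Appendix I.1, Q11 asks for how many patients the HCP has prescribed U-200 or managed treatment with it. The answer 0 carries the instruction "TERMINATE AFTER QUESTION 14 IF 140 OR MORE COMPLETE RESPONDENTS HAVE ANSWERED 0", and the number 140 is marked as configurable. Section 5.2 says only that HCPs with and without prescribing experience will be included. Sections 5.7, 5.9 and 5.11 do not mention the quota. The only HCP subgroup analysis named in Section 5.9 is by medical specialty.

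**The concern.** Random invitation does not make the people who choose to answer a random sample. Section 5.11 admits self-selection but leaves the claims in Sections 4, 5.1 and 5.7 standing, and it repeats one of them for HCPs. A reader of the final report would take the interval as covering the distance from the truth in the target population, when it covers sampling error only.

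The quota is a different problem from non-response. It fixes the composition of the HCP sample by design. If HCPs without U-200 patients are more than half of those eligible and willing, the pooled HCP rate depends partly on a configurable setting in the questionnaire. HCPs who have used the product may well know the messages better than those who have not, so pooling the two groups in a proportion set by quota could move the headline comprehension figure by as much as the stated precision.

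**Working it through.** **1. The plan's own figure.** Equation 1 with n = 280 is 1.96 × √[p(1 − p)/280]. It gives 5.86, 5.74, 5.37, 4.69 and 3.51 points at p = 50, 60, 70, 80 and 90%. Table 1 states 5.9, 5.7, 5.4, 4.7 and 3.5, so it reproduces after rounding. The formula contains no term for selection.

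**2. Quota effect (HCP survey only).** Inputs from the protocol are the quota of 140 and the total of 280, so the sample is half zero-patient HCPs once the quota binds and the target is met. Two inputs are not given and are assumed:
- s, the share answering 0 at Q11 among eligible HCP respondents without a quota;
- d, the percent correct among HCPs with one or more U-200 patients minus the percent correct among those with none.

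The pooled rate under the quota differs from the rate without it by (s − 0.5) × d.

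| s | d = 10 | d = 20 | d = 30 |
|---|---|---|---|
| 50% or less | 0 | 0 | 0 |
| 70% | 2.0 | 4.0 | 6.0 |
| 80% | 3.0 | 6.0 | 9.0 |
| 90% | 4.0 | 8.0 | 12.0 |

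At s = 80%, a gap of 5.9/0.3 = 19.7 points makes the shift equal to the largest half-width in Table 1.

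**3. Non-response (both surveys).** Bias = (1 − r) × g, where r is the response rate and g is the respondent rate minus the non-respondent rate. The protocol gives neither. The gap at which the bias equals the half-width h is h/(1 − r):

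| r (assumed) | h = 5.9 | h = 4.7 | h = 3.5 |
|---|---|---|---|
| 5% | 6.2 | 4.9 | 3.7 |
| 10% | 6.6 | 5.2 | 3.9 |
| 20% | 7.4 | 5.9 | 4.4 |
| 30% | 8.4 | 6.7 | 5.0 |
| 50% | 11.8 | 9.4 | 7.0 |
| 70% | 19.7 | 15.7 | 11.7 |

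For r between 5% and 30% the gap needed is therefore about 4 to 8 points. At 50% or above it is considerably larger.

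**4. What bias does to the interval.** Summing exact binomial probabilities at n = 280 with a true rate of 80%, the Equation 1 interval covers the truth 94.3% of the time with no bias, 75.7% with +2.5 points and 33.2% with +5 points. A larger sample narrows the interval but leaves the bias unchanged.

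**5. Whether the quota can be undone.** HCPs stopped by the quota still answer through Q14. Management of diabetes (Q5), awareness (Q10), Q11 itself and the employment exclusion (Q12) are therefore recorded for them. The share answering 0 among all screened HCPs who otherwise qualify can be observed and used as a weight.

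**The case against.** The protocol is open about self-selection. It uses payment, reminders and two survey modes to encourage response, and it plans to report "The number of survey invitations issued by method of distribution and specialty" together with responders, eligible and ineligible HCPs, and completers. The study is descriptive, Section 5.7 sets no target rate, and the criterion in Section 5.3 refers to a majority of respondents. A 6-point upward shift would change a majority verdict only if the observed rate lay between 50% and 56%. The quota may never bind. It also has a purpose: the discussion items Q20 and Q21 are not shown to HCPs answering 0, so it protects their denominator. All of this stands, and it limits the consequence. It does not remove the wording in Sections 4, 5.1 and 5.7, which concerns populations and not respondents.

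A reader might infer four stronger points that the documents do not support:
- *The estimates are biased upward by more than the stated precision.* The protocol gives no response rate and no knowledge gap. An upward direction is plausible but not shown.
- *The plan omits a non-response analysis.* A comparison of respondents with those invited may sit in the analysis plan, which is not at hand, so its absence is not a finding.
- *Screening out HCPs unaware of the product is an error.* It is the stated eligibility rule in Sections 5.2 and 5.4.1.
- *Weighting by specialty, age, sex or state would cure non-response.* It would not remove a difference in engagement within those groups. Registered nurses and those in other roles skip the specialty question (Q7), so they could not be placed in a specialty group.

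**Conclusion.** The point holds as a mismatch between what the protocol claims and what its design can deliver. Sections 4, 5.1 and 5.7, and the second sentence of Section 5.11, claim representativeness, generalization or a population bound that self-selected completers cannot provide. Table 1 is arithmetically correct but covers sampling error only.

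The quota is a separate effect. It is confined to HCPs, is not mentioned in the sections that describe the sample, its size, its analysis or its limitations, and acts only if more than half of eligible HCP respondents answer 0. Its size is (s − 0.5) × d: zero at s of 50% or less, and 6 points at the assumed s = 80% and d = 20, against half-widths of 3.5 to 5.9. It concerns HCPs who neither prescribed U-200 nor managed treatment with it, a narrower group than non-prescribers.

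Non-response bias is of unknown size. It can be said to match the stated half-width only under an assumed 5–30% response and a gap of about 4 to 8 points.

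**What to change.** 1. **Wording.** In Section 4, replace the statement about a representative population and generalization with inference limited to eligible HCPs and patients who respond. Do the same for the population-rate sentence in Section 5.7, and state there that Table 1 covers sampling error only. Bring Section 5.1 and the second sentence of Section 5.11 into line.
2. **Disclosure.** Describe the Q11 quota, including that 140 is configurable, in Sections 5.2, 5.7 and 5.11.
3. **Analysis, Section 5.9.** Report HCP comprehension separately for Q11 = 0 and Q11 of 1 or more. Beside the pooled rate, show an estimate weighted to the Q11 share among all screened HCPs who otherwise meet eligibility, including those stopped by the quota. This removes the quota effect but not non-response bias.

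**Cost.** The wording and disclosure cost nothing in data, and the weights come from answers already collected. The price is precision. With 140 per group, the half-width for each group is 8.3 points at 50%, 6.6 at 80% and 5.0 at 90%. For the weighted estimate, take an assumed 80/20 split with 60% correct among zero-patient HCPs and 85% among the others. The weighted rate is 0.8 × 60 + 0.2 × 85 = 65%, with half-width 1.96 × √[(0.64 × 0.24 + 0.04 × 0.1275)/140] = 6.6 points. The pooled rate is 72.5%, with half-width 1.96 × √[0.725 × 0.275/280] = 5.2 points. The weighted interval is thus about 26% wider, treating the observed Q11 share as known.

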5. RESEARCH METHODS

5.1. Study Design

This study will be observational and cross-sectional in design. Separate surveys will be administered to HCPs involved in the treatment and management of patients with diabetes and to patients with diabetes who have been prescribed Humalog U-200 KwikPen. The study has been designed and will be executed and analyzed in collaboration with United BioSource Corporation (UBC). The surveys have been developed to enable the study objectives to be met.

Qualitative Research (also known as User Testing) was performed on each survey with a sample of 12 HCPs and 9 patients. The Qualitative Research procedure was designed to assess comprehension among patients regarding the words and phrases used in select survey questions and response options. Qualitative Research also assessed the clarity of the survey questions as presented to HCPs and the interest and acceptance of the surveys among all prospective respondents, flow and ease of completing the surveys, and preferred modes of administration. Findings and recommendations from Qualitative Research have been incorporated into the surveys

Assessment of the additional risk minimization measures in the participating samples will be used to determine whether the target populations are aware of and adherent to the key safety message themes regarding the risk of hypoglycemia and/or hyperglycemia attributed to medication errors or misuse associated with the administration of Humalog U-200 KwikPen. All statistical analyses will be descriptive, i.e., no formal hypothesis will be tested.

HCPs:

HCPs will be identified through Lilly's list of HCPs who were targeted for the DHPC. Surveys targeting eligible HCPs will be administered via two modalities: 1) Internet, which will allow respondents to participate at a time and location that is convenient for them, or 2) by telephone to allow participation by respondents who may not have Internet access. Each invitation will

include information on how to access the online survey and provide the toll-free number for accessing the telephone survey. Both modalities will offer the same survey.

All HCPs who complete all survey questions and who provide their contact information will be compensated \$100 in the form of a gift card to thank them for their time and effort. HCPs who choose to participate and complete a survey and are licensed and practice in Massachusetts, Minnesota, Vermont, or the District of Columbia will not receive compensation in accordance with state laws. HCPs will be informed that if they are from these states and are eligible to participate, they will not receive compensation for their time or effort. The mailing will also include a Thank You Letter, a copy of the DHPC on the correct use of Humalog U-200 KwikPen (insulin lispro) and a copy of the correct answers to key safety message questions. Respondent-identifying information will be collected by UBC for the purposes of providing payment only.

Patients:

Patients will be identified through a Pharmacy Benefits Manager (PBM) partner, which will provide broad demographic coverage and include patients in 50 states and the District of Columbia. Surveys targeting eligible patients will be administered via two modalities: 1) the Internet, which will allow respondents to participate at a time and location that is convenient for them, or 2) by telephone, which will allow participation of respondents who do not have Internet access or who are not computer literate. Each invitation will include information on how to access the online survey and will provide the toll-free number for accessing the telephone survey. Both modalities will offer the same survey.

All respondents who complete a survey and who provide their contact information will be provided \$20 in the form of a gift card to thank them for their time and effort. The mailing will also include a Thank You Letter, a copy of the Patient Information Letter/*IMPORTANT SAFETY INFORMATION* for Humalog U-200 KwikPen (insulin lispro) and a copy of the correct answers to key safety message questions. Respondent-identifying information will be collected by UBC for the purposes of providing payment only.

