Humalog U-200 KwikPen is a prefilled and multi-dose pen-injector device (pen) that delivers insulin lispro by subcutaneous injection to improve glycemic control in adults and children with diabetes mellitus. Compared to Humalog U-100 KwikPen, it contains the same number of units of insulin lispro in half the volume. Despite warning messages on the pen and in the instructions for use, results from Human Factors studies performed in the United States (US) showed that a small percentage of patients may choose to withdraw insulin from the pen cartridge with a syringe if faced with device malfunction. Anecdotal information also indicates that patients may transfer insulin lispro from the pen cartridge into an insulin pump. Because of these data and to further optimize the benefit-risk balance of the presentation, additional Risk Minimization Measures beyond routine risk minimization measures (are being implemented, including communications to Healthcare Professionals (HCPs) and patients to minimize the risk of hyperglycemia and/or potentially hypoglycemia associated with insulin transfer from the pen cartridge to an alternative administration device without concentration adjustment and dose adjustment when transferring from Humalog U-100 KwikPen to Humalog U-200 KwikPen.

The additional Risk Minimization Measures will include a Direct Healthcare Professional Communication (DHPC) that will be distributed to pharmacists and prescribers (endocrinologists and mealtime insulin prescribing primary care physicians, nurse practitioners, and physician's

assistants). A patient communication document will be distributed in the single pen product sample packages that are routinely provided by HCPs to patients who have been newly prescribed Humalog U-200 KwikPen.

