5.4. Setting

The assessment surveys will be executed and the analysis will be completed within 18 months from product launch.

HCPs:

Eligible HCPs will receive an invitation letter ([APPENDIX I.2](#)) via email if an email address is available, or a letter via the United States Postal Service (USPS). The invitation letter will include: an overview of the rationale for the survey, information on how to access the survey online and by telephone, and a unique User Identification to ensure that the invitation is used only once. For telephone interviews, a trained interviewer, working from a computer-assisted telephone interviewing (CATI) script, will read questions or statements to the HCP. The letter will also contain a unique code that the respondent must provide when accessing the survey via the Internet or telephone. For telephone interviews, a trained interviewer, working from a computer-CATI script, will read questions or statements to the HCP. The average survey is expected to take approximately 15 minutes to complete.

A random sample of HCPs will be recruited to participate in the survey based on the list of HCPs to whom Lilly has provided a DHPC letter. The recruitment letter will indicate that participants will be compensated \$100 for their time and effort in completing the survey with the exception of HCPs who are licensed and practice in Minnesota, Vermont, Massachusetts or the District of Columbia in accordance with state laws. HCPs from these states can elect to participate however they will not be paid. Respondent-identifying information will be collected for the purposes of providing payment.

The response rate will be monitored throughout the data collection period. Reminder notices will be sent via email and or via the USPS. Additional recruitment methods may be explored during survey execution if necessary to achieve a total of 280 completed surveys.

Patients:

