5.6. Data sources

In this survey, the data source for HCPs will be Lilly's list of HCPs who received the DHPC. From this data source HCPs will be invited to participate in the survey. The data source for patients will be the PBM's prescription data identifying those patients who have filled/refilled a prescription of Humalog U-200 KwikPen within 90 days prior to survey launch.

Structured questionnaires ([APPENDIX I.1](#) and [APPENDIX I.3](#)) comprised of closed-ended questions or statements with multiple response choices (i.e., questions or statements asking the respondents to choose from a defined list of responses) will be used to collect the survey data. The surveys will collect data on respondent characteristics and their responses to the risk understanding questions. The data collected from the surveys will be used to inform the evaluation of the effectiveness of the risk minimization measures.

Each survey will begin with a screening module with questions to confirm eligibility. Depending on the answers to the screening questions, survey participation will either be terminated or continued. If ineligible, the respondent is immediately notified with a "thank you" message that survey participation has ended. If eligible, the respondent is allowed to continue survey participation.

HCPs:

Screening questions:

- Agreement to participate
- Involved in the management of patients with diabetes
- Employment by Lilly, UBC, or the FDA
- Awareness of Humalog U-200 KwikPen

Data on demographic characteristics:

- Age
- Gender
- Role at facility
- Facility type
- State of practice

- HCP medical specialty (e.g., endocrinology, primary care)
- Number of years practicing medicine/nursing
- Number of Humalog U-200 KwikPen-treated patients the HCPs prescribed to or managed in the 12 month period preceding the survey (self-reported)

Data pertaining to evaluation of the effectiveness of the risk minimization measures:

The survey includes questions/statements that will assess the understanding or the risks and associated behavior of the HCPs to minimize these risks. The understanding level and behaviors will be analyzed using descriptive statistics and confidence intervals (CIs) and will be used to determine the effectiveness of the risk minimization measures:

- Awareness of the DHPC on the correct use of Humalog U-200 KwikPen
- Understanding of the key safety messages

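### The HCP rates have one denominator, but the protocol describes the population behind it in four non-equivalent ways, and the survey's role options do not match the DHPC audience

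*Protocol*

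**What the plan says.** The protocol describes the source of HCP respondents four times:

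- Section 5.1: "HCPs will be identified through Lilly's list of HCPs who were targeted for the DHPC".
- Section 5.4: the random sample is drawn "based on the list of HCPs to whom Lilly has provided a DHPC letter".
- Section 5.6: "the data source for HCPs will be Lilly's list of HCPs who received the DHPC".
- Section 5.11: "a random sample of HCPs who received educational outreach", which the same sentence then extends to HCPs who have been educated about the product.

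Section 3.1 gives the DHPC audience. The letter is to be "distributed to pharmacists and prescribers (endocrinologists and mealtime insulin prescribing primary care physicians, nurse practitioners" and physician's assistants). In Appendix I.1, Q5 accepts an HCP whose only involvement is patient education. Q6 offers physician, nurse practitioner, physician assistant, "Registered Nurse" and Other. The last two skip the specialty question and continue. Pharmacist is not an option. Q16 then asks every eligible respondent about awareness of the DHPC and words it as a letter that the respondent was given.

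The inclusion criteria in 5.4.1 require awareness of the product and involvement in diabetes care, not receipt of the DHPC. Section 6.2 limits the analysis to completed surveys, and 5.7 plans 280 of them.

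**The concern.** The four descriptions select different people. A list of those targeted keeps HCPs whose letter never arrived. A list of those who received it drops them. A list of those given educational outreach suggests a better-informed group. Section 5.6 uses DHPC awareness and understanding of the safety messages to judge whether the measures worked, so the reader has to know which group the percentages describe.

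The role mismatch raises the same question among respondents. A registered nurse, outside the stated audience, enters the pooled rates. A pharmacist, inside it, can be recorded only as Other and so cannot be recognised. If Q16 is answered no, the data cannot show whether the letter was not sent, not delivered or not remembered.

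**Working it through.** **1. The plan's own figure.** Inputs are n = 280, two-sided 95%, and Equation 1 (5.7): half-width = 1.96 × √(p(1−p)/280). At p = 50, 60, 70, 80 and 90% this gives 5.86, 5.74, 5.37, 4.69 and 3.51 points. Table 1 shows 5.9, 5.7, 5.4, 4.7 and 3.5. It reproduces, and nothing in this point alters it.

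**2. The frame wordings against the non-receipt rule.** Section 5.11 says that a respondent who reports not having received the communication is evidence of imperfect dissemination.

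| Frame | Contains true non-receivers? | What a no to Q16 can mean |
|---|---|---|
| Targeted (5.1) | Yes | Not delivered, or not noticed or remembered |
| Provided (5.4) | Yes, if provided means sent | The same |
| Received (5.6) | No | Only not noticed or remembered |
| Educational outreach (5.11) | Not stated; link to the DHPC not given | Cannot be determined |

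On a received frame, real delivery failures are removed before the survey starts, so the 5.11 rule can no longer detect them. The rule makes sense only on a targeted or sent frame.

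**3. Roles.**

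| Role | DHPC audience in 3.1 | Q6 |
|---|---|---|
| Physician (endocrinology, or primary care prescribing mealtime insulin) | Yes | Own option |
| Nurse practitioner, physician assistant | Yes, if prescribing mealtime insulin in primary care | Own option |
| Pharmacist | Yes | None; only Other |
| Registered nurse | Not listed | Own option; continues |

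The mismatch runs in both directions.

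**4. How far the rates could move.** The protocol gives no delivery rate and no role shares. Let r be the share of completers actually reached by the DHPC, **assumed** at 70% to 100%. Three further assumptions: awareness is 70% among those reached and 0% among the rest; understanding is 80% among those reached; and it is 50% among the rest.

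- Awareness over all completers = 0.70 × r
- Understanding over all completers = 0.80 × r + 0.50 × (1 − r)
- Half-width among those reached = 1.96 × √(0.25/(280r)), at an observed 50%

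| r | Awareness | Understanding | n reached | Half-width at 50% |
|---|---|---|---|---|
| 100% | 70% | 80% | 280 | 5.9 |
| 90% | 63% | 77% | 252 | 6.2 |
| 80% | 56% | 74% | 224 | 6.5 |
| 70% | 49% | 71% | 196 | 7.0 |

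At r = 90%, awareness moves 70 − 63 = 7 points, more than the Table 1 half-width of 5.4 at 70%. Understanding moves 80 − 77 = 3 points, less than the half-width of 4.7 at 80%. At r = 80% it moves 6 points, which is more. No confidence interval reflects a shift of this kind.

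**The case against.** The strongest reply is that this is loose wording about one list. Sections 5.1 and 5.6 both refer to the sponsor's list, and nothing says that delivery was confirmed or that failures were removed. That is fair: the protocol does not show that several lists exist. But the wordings still disagree on who is on the list, and 5.11 generalises from the most favourable of them.

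Some stronger readings are tempting and do not stand:

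- A reader might infer that the rates have no single denominator. They have one: completed surveys of eligible HCPs (6.2), with Q15 and Q16 put to every eligible respondent.
- A reader might infer that registered nurses in the survey were never sent the DHPC, or used someone else's code. Sections 5.4 and 5.11.1 restrict entry to invitees with a single-use code. The documents show only that Q6 and 3.1 disagree. A nurse on the list would mean that 3.1 is incomplete.
- A reader might infer that a fall of DHPC awareness below 50% fails the study's criterion. The majority criterion in 5.3 concerns awareness of the key safety messages and sets no line for DHPC awareness.

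It can also be said that Q6 records role, so a table by role needs no new data, and that the planned specialty analysis already leaves out nurses and Other because both skip Q7. Both statements are true. But that analysis would also leave out any pharmacist, and no later analysis can recover pharmacists from Other or change which list was sampled.

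**Conclusion.** The point holds as a contradiction about the target population together with a two-way mismatch between survey roles and DHPC audience. It affects what the HCP rates may be said to represent, not how they are calculated. The contradiction and the mismatch follow from the text alone.

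The size of any effect is unknown. The illustration (awareness reading as 49% to 70%, understanding as 71% to 80%) rests wholly on the assumed r and the assumed rates in each group, including that nobody missed by the letter is aware of it. Section 5.11 itself allows that respondents may understand the risks without having received the communication, so the effect on understanding, the primary objective, could be smaller than shown. The correction is worth making because it is cheap and because the frame must be settled before the sample is drawn.

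**What to change.** 1. Use one frame in 5.1, 5.4, 5.6 and 5.11: all HCPs on the list targeted for the DHPC, whether or not delivery was confirmed. Rewrite the generalisation in 5.11 so that it refers to that population and not to HCPs already educated about the product.
2. Add a pharmacist option to Q6, with its own routing, and adapt Q8, which names only physicians, physician assistants and nurses.
3. Report DHPC awareness and understanding for respondents in the roles listed in 3.1. Put registered nurses and the remaining Other respondents in a separate descriptive table.
4. Do not terminate registered nurses. Sections 5.2 and 5.4.1 admit any product-aware HCP involved in diabetes care, and nurses can usefully answer Q20 and Q21, which ask what anyone at the practice discusses with patients. Do not drop Other on the present Q6 either, because it may contain pharmacists who were sent the letter.

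The cost is wording in four sections, one added response option with its routing, the Q8 edit and one extra table. The audience-role rates rest on fewer respondents than the 280 planned: if 90% of completers were in those roles, n = 252 and the half-width at 50% is 6.2 points instead of 5.9. Measured DHPC awareness may also be lower on the full targeted frame.
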